DDI	Drug-drug interaction
DM	Dermatomyositis
DMC	Data Monitoring Committee
DNA	Deoxyribonucleic acid
DOI	Definition of Improvement
ECG	Electrocardiogram
eCRF	Electronic case report form
EDC	Electronic data capture
ELISA	Enzyme-linked immunosorbent assay
EOS	End of Study
EOT	End of treatment
EQ-5D-5L	EuroQol 5-dimension 5-level
EQ-VAS	EuroQol visual analog scale
ETV	Early Termination Visit
EULAR	European League Against Rheumatism
FAS	Full Analysis Set
FDA	Food and Drug Administration

Abbreviation or Term	Definition
FI-2	Functional Index-2
FSH	Follicle stimulating hormone
GCP	Good Clinical Practice
GLP	Good Laboratory Practice
GMP	Good Manufacturing Practice
HAQ-DI	Health Assessment Questionnaire-Disability Index
hCG	Beta-human chorionic gonadotropin
ICF	Informed consent form
ICH	International Council for Harmonisation
I/E	Inclusion/Exclusion
IEC	Independent Ethics Committee
IFU	Instructions for Use
IgG	Immunoglobulin G
IMACS	International Myositis Assessment and Clinical Studies Group
IV	Intravenous
IRB	Institutional Review Board
ISR	Injection site reaction
LDH	Lactate dehydrogenase
LMP	Low-molecular mass polypeptide
LN	Lupus nephritis
MDAAT	Myositis Disease Activity Assessment Tool
MDGA	Physician Global Assessment
MDGIC	Physician Global Impression of Change
MDI	Myositis Damage Index
MECL-1	Multicatalytic endopeptidase complex-like 1
MedDRA	Medical Dictionary for Regulatory Activities
MITAX	Myositis Intention to Treat Activity Index
MMF	Mycophenolate mofetil
MMT-8	Manual Muscle Testing-8 Muscle Groups
MYOACT	Myositis Disease Activity Assessment Visual Analogue Scales
NCI-CTCAE	National Cancer Institute Common Terminology Criteria for Adverse Events
NRS	Numerical Rating Scale
PBMC	Peripheral blood mononuclear cell
PD	Pharmacodynamic
PFS	Pre-filled syringe
PGIC	Patient Global Impression of Change

Abbreviation or Term	Definition
P-gp	P-glycoprotein
PK	Pharmacokinetic
PM	Polymyositis
PP	Per protocol
PROM	Patient-reported outcome measure
PtGADA	Patient Global Assessments of Disease Activity
PtGADD	Patient Global Assessments of Disease Damage
RA	Rheumatoid arthritis
RNA	Ribonucleic acid
SAE	Serious adverse event
SAP	Statistical analysis plan
SC	Subcutaneous
SD	Standard deviation
SLE	Systemic lupus erythematosus
STS	Sit-to-stand
SUSAR	Suspected unexpected serious adverse reaction
TEAE	Treatment-emergent adverse event
Th	T helper cell
T-L	Trypsin-like
TIS	Total Improvement Score
Treg	Regulatory T cell
US	United States
VAS	Visual analog scale
WFI	Water for injection
WHO	World Health Organization
WOCBP	Women of childbearing potential

1. INTRODUCTION

Study KZR-616-003E is an open-label extension of the Phase 2 study KZR-616-003, which is a randomized, double-blind, placebo-controlled crossover study to evaluate the efficacy and safety of KZR-616 in the treatment of patients with active polymyositis (PM) or dermatomyositis (DM).

1.1. 26S Proteasome Background

The 26S proteasome is a ubiquitously expressed protein complex responsible for the homeostatic control of protein turnover and regulated degradation of proteins involved in most cellular functions (Ciechanover 2012; Coux 1996; Wilk 1983). Each proteasome contains a 20S core, containing 2 copies of 3 distinct proteolytic enzymes, and 2 regulatory caps forming a 26S complex.

The proteasome exists in 2 forms: the constitutive proteasome and the immunoproteasome. The constitutive proteasome is expressed ubiquitously throughout the body and is responsible for protein degradation in tissues such as the heart, kidney, and liver. In the constitutive proteasome, proteolytic activities are encoded in the β 5, β 1, and β 2 subunits and are characterized based on substrate specificity as chymotrypsin-like (CT-L), caspase-like (C-L) and trypsin-like (T-L), respectively. The immunoproteasome is expressed primarily in hematopoietic cells (eg, lymphocytes and monocytes), and is induced in cytokine-exposed nonhematopoietic cells (Glynne 1991; Martinez 1991; Nandi 1996). In the immunoproteasome, low-molecular mass polypeptide (LMP) 7, LMP2, and multicatalytic endopeptidase complex-like 1 (MECL-1) replace the β 5, β 1, and β 2 subunits of the constitutive proteasome, respectively. Low-molecular mass polypeptide 7 has a similar substrate preference as β 5 and is thus referred to as the CT-L subunit of the immunoproteasome.

The proteasome has been validated as a therapeutic drug target through regulatory approval of 3 compounds, bortezomib (VELCADE[®]), carfilzomib (KYPROLIS[®]), and ixazomib (NINLARO[®]), for use in the treatment of the plasma cell neoplasm, multiple myeloma. These compounds all show equivalent potency for the β 5 subunit of the constitutive proteasome and the LMP7 subunit of the immunoproteasome (Kirk 2012; Kisselev 2012). This dual-targeting nature is necessary for their ability to induce cytotoxicity in multiple myeloma cells and other cell types. Selective inhibitors of LMP7 or β 5 alone have no cytotoxic potential (Parlati 2009).

1.2. Proteasome Inhibitors for the Treatment of Inflammatory Disorders

The proteasome has been posited as a target for drug development in chronic inflammatory conditions and autoimmune disorders (Elliott 2003). Bortezomib, a constitutive or dual-targeting proteasome inhibitor, blocks cytokine release from immune effector cells and has demonstrated anti-inflammatory activity in several animal models of autoimmune disorders including rheumatoid arthritis (RA) (Palombella 1998) and systemic lupus erythematosus (SLE) (Neubert 2008). More recently, bortezomib was shown to have rapid clinical activity in patients with refractory SLE and lupus nephritis (LN) who had failed standard immunosuppressive therapies (Alexander 2015; Zhang 2017; de Groot 2015). However, systemic toxicities associated with dual-targeting proteasome inhibition, such as anemia and thrombocytopenia, restrict chronic administration (Bross 2004). Further, bortezomib is associated with a

dose-limiting side effect of peripheral neuropathy, likely caused by off-target inhibition of the serine protease HtrA2 in neurons (Arastu-Kapur 2011). Peripheral neuropathy is not induced by peptide ketoepoxide proteasome inhibitors such as carfilzomib (Arastu-Kapur 2011; Dimopoulos 2016).

The discovery of PR-957 (now called ONX 0914), a selective immunoproteasome inhibitor, demonstrated that the immunomodulatory and anti-inflammatory effects of dual-targeting proteasome inhibitors are due to inhibition of immunoproteasome activity in immune effector cells and inflamed tissues (Ichikawa 2012; Muchamuel 2009). ONX 0914 is a tripeptide ketoepoxide analog of carfilzomib that selectively inhibits the immunoproteasome in vitro and upon administration to mice. ONX 0914 exposure inhibited cytokine production in immune effector cells, reduced the number and activity of inflammatory T cell subsets such as T helper (Th) cells 1 and Th17, increased the number of regulatory T cells (Treg), and blocked autoantibody formation (Ichikawa 2012; Muchamuel 2009; Kalim 2012). ONX 0914 was shown to be therapeutically active in mouse models of SLE, in which it demonstrated equivalent activity but better tolerability than bortezomib (Ichikawa 2012; Kalim 2012). In addition, treatment of mice with ONX 0914 did not reduce the number of splenic lymphocytes or impair viral clearance in multiple infection models (Muchamuel 2009; Mundt 2016).

1.3. KZR-616 Background

KZR-616 is a tripeptide ketoepoxide that is an analog of both ONX 0914 and the United States (US) Food and Drug Administration (FDA)-approved agent carfilzomib. KZR-616 was developed in a medicinal chemistry effort to optimize potency and selectivity for multiple immunoproteasome subunits. KZR-616 demonstrates potent and selective inhibition of the LMP7 subunit of the immunoproteasome and targets multiple subunits of the immunoproteasome at therapeutically relevant concentrations. KZR-616 has no apparent off-target activities, no significant signals in safety pharmacology studies, and no apparent genotoxic potential.

KZR-616 blocks cytokine production across multiple immune cell types, reduces the activity of inflammatory Th cell subsets, and blocks plasma cell formation and autoantibody production. In mouse models of SLE and LN, KZR-616 treatment improved renal function in diseased animals and dramatically reduced tissue damage and leukocyte infiltration in kidneys. In addition, combining KZR-616 with mycophenolate mofetil (MMF) improved the therapeutic response versus either treatment alone in the same mouse models. The pharmacokinetics (PK) and metabolic properties of KZR-616 in preclinical models indicate little risk for drug-drug interactions (DDIs) and are similar to carfilzomib, an agent which has been shown to have little to no DDI risk (Wang 2013). In both range-finding and Good Laboratory Practice (GLP)-compliant toxicity studies, KZR-616 was well tolerated at doses that resulted in selective and potent inhibition of the immunoproteasome.

The safety, PK, and proteasome inhibition level of KZR-616 has been studied in healthy volunteers in 2 Phase 1 trials, KZR-616-001 and KZR-616-004. Subcutaneous (SC) administration of KZR-616 was well tolerated at doses that resulted in potent and selective inhibition of the immunoproteasome, but not the constitutive proteasome. Adverse events (AEs) were generally mild and transient and were predominantly injection site reactions (ISRs) such as erythema, induration, and tenderness (pain). Treatment with KZR-616 for 4 weeks did not appear

to result in persistent laboratory abnormalities as commonly seen with the dual-targeting proteasome inhibitors (eg, thrombocytopenia, anemia, and neutropenia).

Subcutaneous administration of KZR-616 resulted in consistent, dose-proportional PK. At all dose levels tested, KZR-616 was rapidly absorbed and cleared with no accumulation following weekly repeat doses. Drug levels were below the limit of quantitation by 24 hours post dose. The pharmacology was consistent across subjects, with low inter-subject variability in both exposure and target inhibition, regardless of concomitant treatment with or without corticosteroids and antihistamines. Though KZR-616 is a weak time-dependent inhibitor of Cytochrome P450 (CYP) 3A4 and a substrate of P-glycoprotein (P-gp), the rapid clearance and extrahepatic metabolism of KZR-616 by epoxide hydrolases strongly suggest that there is minimal risk for a DDI.

Across a dose range from 7.5 to 75 mg, SC administration of KZR-616 resulted in selective and dose-dependent inhibition of peripheral blood mononuclear cell (PBMC) CT-L activity (predominantly immunoproteasome), with doses of ≥ 30 mg resulting in mean inhibition of PBMC CT-L activity $>80\%$ and mean inhibition of whole blood CT-L activity (predominantly constitutive proteasome) $\leq 36\%$. Data further showed that despite incomplete recovery of immunoproteasome activity on Day 7 (6 days after dosing), there was not an accumulation of proteasome inhibition. From a PK and pharmacodynamic (PD) perspective, weekly SC administration of KZR-616 appeared equivalent to serial episodic dosing.

1.4. Rationale for Use of KZR-616 in the Proposed Study Populations, and Rationale for the Study

Idiopathic inflammatory myopathies such as PM and DM are characterized by inflammatory infiltrates in the skeletal muscle. Innate and adaptive immune mechanisms (eg, macrophages, autoreactive lymphocytes, autoantibodies, pro-inflammatory cytokine production) and intrinsic defects in skeletal muscle contribute to muscle weakness and damage in myositis. For example, Treg are considered instrumental for healing via interactions with muscle stem cells, whereas accumulation of cluster of differentiation (CD)4+ and CD8+ T lymphocytes are associated with further immune-mediated injury, as occurs in inflammatory myositis and some muscular dystrophies ([Sciorati 2016](#)). The immunoproteasome has also been shown to be upregulated in the muscle of patients with PM and DM and the skin of patients with DM ([Bhattarai 2016](#); [Ghannan 2014](#)). Further, increased levels of circulating proteasomes, likely reflecting immunoproteasomes, have been observed in patients with inflammatory myositis and appear to be associated with disease markers such as creatine kinase (CK) and myoglobin levels ([Egerer 2002](#)).

In vitro, KZR-616 and other immunoproteasome inhibitors block cytokine production across multiple immune cell types, reduce the activity of inflammatory Th cell subsets, increase the number of Treg cells, and block plasma cell formation and autoantibody production ([Ichikawa 2012](#); [Kalim 2012](#); [Muchamuel 2009](#)). KZR-616 does not induce cytotoxicity in vitro, has demonstrated promising therapeutic activity in animal models of RA and SLE/LN. In particular, in a C-protein induced myositis (CIM) model, KZR-616 treatment improved grip strength in diseased mice, which correlated with reduced serum levels of CK and reduced tissue damage and lymphocytic infiltration of the triceps and gastrocnemius muscles. Of note, grip

strength in the diseased mice treated with KZR-616 was equivalent to age-matched control animals in which myositis had not been induced (data on file).

Because of the promising nonclinical characteristics of KZR-616, along with its favorable safety profile in healthy volunteers, KZR-616 represents a new agent with a novel mechanism of action that may have broad therapeutic potential across autoimmune conditions, including PM and DM. As patients exist who have an inadequate response to currently available treatments, an unmet medical need remains for new therapies for the treatment of PM and DM.

This open-label study was designed to allow up to 96 weeks of additional treatment with KZR-616, which will allow for assessment of the durability of therapeutic response and evaluation of longer-term improvement in the symptoms of PM and DM.

1.5. Rationale for Study Endpoints

The Myositis Response Criteria are recommended for use as primary endpoints in myositis therapeutic trials. The criteria use core set activity measures (CSAMs) from the International Myositis Assessment and Clinical Studies Group (IMACS). By combining the absolute percentage change in these 6 core set measures (each with varying weights), a Total Improvement Score (TIS), ranging from 0 to 100, is obtained. The IMACS CSAMs consist of:

- Manual Muscle Testing-8 Muscle Groups (MMT-8)
- Physician Global Assessment (MDGA)
- Patient Global Assessments of Disease Activity (PtGADA)
- Health Assessment Questionnaire-Disability Index (HAQ-DI)
- Muscle enzymes (clinical laboratory assessments): CK, aldolase, lactate dehydrogenase (LDH), alanine aminotransferase (ALT), and aspartate aminotransferase (AST)
- Myositis Disease Activity Assessment Tool (MDAAT, 2005 version)

In addition, IMACS has defined the following core set damage measures (CSDMs):

- Myositis Damage Index (MDI)
- Patient Global Assessment of Disease Damage (PtGADD)

Mean change from start to end of KZR-616 treatment was the primary efficacy endpoint for Study KZR-616-003, and secondary and exploratory endpoints utilized the CSAMs and CSDMs, along with other measures of function and outcomes. To determine long-term efficacy in the same patient population, many of the endpoints used in Study KZR-616-003 will also be used in this study with consideration for treatment periods (see [Section 10](#)).

1.6. Summary of Potential Risks and Benefits

KZR-616 is a selective and irreversible inhibitor of the immunoproteasome, a key intracellular function in immune effector cells. Selective inhibition of the immunoproteasome is

immunomodulatory rather than immunosuppressive in preclinical models. KZR-616 is demonstrated to have marked ability to block the inflammatory response in multiple mouse models of autoimmune disease, including but not limited to, models of RA, the progression of nephritis in 2 mouse models of SLE, and in the CIM mouse model of myositis.

KZR-616 is an investigational agent. To date, 2 studies in healthy volunteers using doses ranging from 7.5 to 75 mg KZR-616 weekly have been completed. In addition, a Phase 2 study in patients with SLE with or without LN (KZR-616-002) and a study of patients with PM or DM (KZR-616-003) are ongoing. Adverse events most often associated with KZR-616 to date have been ISRs that are transient, generally mild, and do not appear to increase in severity or frequency with repeat dosing. Tolerability of KZR-616 is improved with an initial 30 mg SC dose of KZR-616, followed by subsequent higher target doses of 45 or 60 mg. It is anticipated that participants in KZR-616-003E will have already demonstrated tolerability to KZR-616 following participation in KZR-616-003. Nonetheless, initial high doses of KZR-616 have been associated with at least one of the following signs/symptoms: hypotension, tachycardia, nausea, vomiting, dizziness, headache, pyrexia, rigors and/or chills.

Based on nonclinical studies with KZR-616, including a mouse model of myositis, the safety of KZR-616 at 45 mg in healthy volunteers, the safety of KZR-616 to date in 46 patients with SLE, and the potential benefit from anti-inflammatory activity induced by immunoproteasome inhibition, the overall positive benefit-risk balance of KZR-616 supports its continued development in patients with PM and DM.

For additional information, please refer to the current version of the KZR-616 Investigator's Brochure.

2. STUDY OBJECTIVES AND ENDPOINTS

2.1. Study Objectives

The efficacy objective is to evaluate the long-term efficacy of KZR-616 in patients with PM or DM.

The safety objective is to evaluate the long-term safety and tolerability of KZR-616 in patients with PM or DM.

2.2. Study Endpoints

2.2.1. Efficacy Endpoints

- Mean change in TIS over time for all patients, for patients with DM only, for patients with PM only, and for patients with a myositis-associated antibody or myositis-specific antibody at the Screening Visit of Study KZR-616-003
- Proportion of patients by TIS response (minimal response = TIS \geq 20, moderate response = TIS \geq 40, major response = TIS \geq 60)
- Proportion of patients meeting IMACS definition of improvement (DOI) over time for patients with baseline core set measures as ascertained at the beginning of KZR-616-003
- Mean change and mean percentage change over time in the IMACS individual CSAMs and CSDMs, stratified by all patients and patients with myositis-associated or myositis-specific antibody at the Screening Visit of Study KZR-616-003
- Mean change over time in the Cutaneous Dermatomyositis Disease Area and Severity Index (CDASI) for all patients with DM, and for patients with DM who have active skin manifestations at baseline of Study KZR-616-003E
- Mean change over time in the MDI
- Mean change over time in muscle enzymes
- Change in proportion and dose of corticosteroid and non-corticosteroid immunosuppressants during Study KZR-616-003E for all patients, and for patients taking corticosteroids or non-corticosteroid immunosuppressants at baseline of Study KZR-616-003E
- Percentage of patients requiring additional medication for myositis treatment during Study KZR-616-003E
- Mean change over time in the EuroQol 5-dimension 5-level (EQ-5D-5L)
- Additional exploratory endpoints (Physician Global Impression of Change [MDGIC], Functional Index-2 [FI-2], Patient Global Impression of Change [PGIC], and Peak Pruritis Numerical Rating Scale [NRS]) will be assessed at multiple time points

As KZR-616-003E is an open-label extension study, additional exploratory endpoints may be conducted, and will be described in the final statistical analysis plan (SAP). Efficacy endpoints may include treatment periods that include data from Study KZR-616-003 based on treatment sequence in that study. See [Section 10](#) for additional details of statistical analyses.

All endpoints, except where noted, will include analyses of all patients, those with DM only, and those with PM only.

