3. STUDY DESIGN

3.1. Type and Design of Study

This is an open-label study to evaluate the long-term efficacy and safety of KZR-616 in patients with active PM or DM who completed the double-blind treatment period of Study KZR-616-003, up to and including the Week 32 Visit, prior to the first dose of open-label KZR-616.

The study design schema is presented in [Figure 1](#).

Patients will be evaluated for eligibility according to the entry criteria (see [Section 4](#)) at, or within 8 weeks after, the Week 32 Visit (ie, the End of Treatment [EOT] Visit [Visit 34]) of Study KZR-616-003. Informed consent may be signed prior to the Week 32 Visit of Study KZR-616-003, and must be signed prior to any study-related activity in KZR-616-003E. For patients who are eligible and willing to enroll in the open-label extension study, the KZR-616-003 Week 32 Visit may also serve as Visit 1 (Day 1) for the open-label extension study. Assessments at this visit performed as part of Study KZR-616-003 will be used as baseline values for the extension study; therefore, these assessments must be performed prior to the first dose of open-label KZR-616 (see [Figure 1](#)).

[figure not shown]
All patients will receive a SC injection of 30 mg KZR-616 at Visit 1 (Day 1), followed by weekly SC injections of 45 mg KZR-616 up to a maximum of 96 weeks. Study drug administration will end for all patients in Study KZR-616-003E when the last patient enrolled has completed 48 weeks of dosing. Patients will have a final follow-up visit 12 weeks after their last dose of KZR-616 (End of Study [EOS] Visit), for a maximum potential length of participation of 108 weeks.

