Safety Population: The safety population will include all patients enrolled who received at least one dose of KZR-616, and will be the population used for the analysis of safety. Adverse event data will be coded to system organ class and preferred term using Medical Dictionary for Regulatory Activities (MedDRA; Version 19.1 or later).

Data will be summarized for the following groups of patients based on the sequence of treatments received in Study KZR-616-003:

Group 1: Arm A (KZR-616:Placebo) from Study KZR-616-003 beginning on Day 1 (first dose of KZR-616) through the end of Study KZR-616-003E

Group 2: Arm B (Placebo:KZR-616) from Study KZR-616-003 beginning on Week 16 (first dose of KZR-616) through the end of Study KZR-616-003E

Groups 1 and 2 combined: from the first dose of KZR-616 in KZR-616-003 through the end of KZR-616-003E

Group 3: Arm B2: Patients receiving KZR-616 from Weeks 16-32 in KZR-616-003 followed by KZR-616 in OLE throughout KZR-616-003E, to evaluate patients who continuously received KZR-616 from KZR-616-003 through KZR-616-003E

Groups 1 and 2 are being assessed for any differences due to the intervening placebo treatment period in Group 1. The rationale for combining Group 1 and Group 2 is to encompass all KZR-616 treatment, and the rationale for assessing Group 3 is to encompass all continuous KZR-616 treatment.

Further details of the statistical methodology, including methods for handling missing data and early withdrawals, will be provided in an SAP that will be finalized prior to database lock. As KZR-616-003E is an open-label extension study, endpoints in addition to those described in [Section 2.2](#) may be conducted as described in the final SAP.

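### Selecting the active-skin DM subgroup at extension baseline understates Arm B's CDASI improvement in summaries that start at the first KZR-616 dose, and filters the two arms differently

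*Combined protocol and SAP*

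**What the plan says.** - **Endpoint.** Section 2.2.1 (and the synopsis) lists "Mean change over time in the Cutaneous Dermatomyositis Disease Area and Severity Index (CDASI) for all patients with DM" and then the same measure "for patients with DM who have active skin manifestations at baseline of Study KZR-616-003E". Neither place defines active skin manifestations or names the visit from which CDASI change is counted.
- **Extension baseline.** Section 3.1, on the Week 32 visit of Study 003: "Assessments at this visit performed as part of Study KZR-616-003 will be used as baseline values for the extension study". Table 1 shows CDASI among the assessments taken over from that visit.
- **Analysis periods.** Section 10 defines Group 1 as "Arm A (KZR-616:Placebo) from Study KZR-616-003 beginning on Day 1 (first dose of KZR-616) through the end of Study KZR-616-003E" and Group 2 as "Arm B (Placebo:KZR-616) from Study KZR-616-003 beginning on Week 16 (first dose of KZR-616) through the end of Study KZR-616-003E". The combined group also starts at first dose. Group 3 is "Patients receiving KZR-616 from Weeks 16-32 in KZR-616-003 followed by KZR-616 in OLE throughout KZR-616-003E".
- **Purpose of the comparison.** Section 10: "Groups 1 and 2 are being assessed for any differences due to the intervening placebo treatment period in Group 1".
- **Other anchors in Section 2.2.1.** Antibody subgroups are fixed at Study 003 screening, and the IMACS definition-of-improvement endpoint uses core set measures from the start of Study 003. The section also allows, without requiring, efficacy endpoints to use treatment periods that reach back into Study 003.

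**The concern.** For any CDASI summary that starts at the first KZR-616 dose, subgroup membership is decided after that start, on the same skin disease that CDASI measures. This conditions on a post-treatment outcome.

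The two arms meet the filter in different states. Arm B is on drug when selected, so patients whose skin has cleared fall out. Arm A is selected after its placebo period, when some or all of an earlier response may have been lost. The subgroups in Groups 1 and 2 could then differ through selection alone, although Section 10 intends to read their difference as an effect of the intervening placebo.

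If change is counted from Week 32 instead, the selection visit is also the reference visit. Regression to the mean then produces apparent improvement.

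At stake is how one descriptive subgroup result is read: whether it can speak to durability or overall skin efficacy in DM patients who had skin disease to treat.

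**Working it through.** **1. Timing.** Arm B: 32 − 16 = 16 weeks of KZR-616, ending at the selection visit. Arm A: drug first, then placebo; from the Week 16 crossover, about 16 weeks of each. Selection therefore comes 16 weeks (Arm B) or 32 weeks (Arm A) after the Section 10 start.

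**2. Plan figures.** The documents give no CDASI mean, SD, cut-off or expected effect, so there is no figure to reproduce. Everything below is illustrative.

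**3. Model (all inputs assumed, in SD units).** X0 is CDASI at first KZR-616 dose, X1 at extension baseline, X2 at an on-drug extension visit. X0 has SD 1 and a mean 1 SD above the active cut-off. The visit-to-visit correlation ρ is 0.5 to 0.9 before drug effects. Individual drug effects have mean d and SD 0.5d. A fraction r of the effect is present at X1 (Arm B r = 1; Arm A r = 0.5 or 0), and the full effect is present at X2.

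- X1 relative to the cut-off: mean m = 1 − rd, variance v = 1 + r²(0.5d)², z = m/√v
- Share kept: Φ(z). Mean excess of those kept over m: E = √v · φ(z)/Φ(z)
- Subgroup change from first dose: −d + [r(0.5d)²/v]·E
- Subgroup change from extension baseline: −(1 − r)d + {[r(1 − r)(0.5d)² − (1 − ρ)]/v}·E

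With d = 1 and ρ = 0.7:

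- Arm B (r = 1): m = 0, v = 1.25, E = 1.118 × 0.399/0.5 = 0.892. From first dose: −1 + (0.25/1.25) × 0.892 = −0.82. From extension baseline: −(0.3/1.25) × 0.892 = −0.21.
- Arm A (r = 0.5): m = 0.5, v = 1.0625, E = 0.533. From first dose: −1 + (0.125/1.0625) × 0.533 = −0.94. From extension baseline: −0.5 + [(0.0625 − 0.3)/1.0625] × 0.533 = −0.62.
- Arm A (r = 0): m = 1, v = 1, E = 0.288. From first dose: −1.00. From extension baseline: −1 − 0.3 × 0.288 = −1.09.

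| | Kept | From first dose: all DM | From first dose: subgroup | From ext. baseline: all DM | From ext. baseline: subgroup |
|---|---|---|---|---|---|
| Arm B | 50% | −1.00 | −0.82 | 0.00 | −0.21 |
| Arm A, half retained | 69% | −1.00 | −0.94 | −0.50 | −0.62 |
| Arm A, none retained | 84% | −1.00 | −1.00 | −1.00 | −1.09 |

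A simulation of 1,000,000 patients per scenario gives the same values to two decimals. With the same true change in both arms, the subgroups differ by 0.94 − 0.82 = 0.12 to 1.00 − 0.82 = 0.18 SD through selection alone.

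Other values for Arm B:

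- d = 0.5: −0.47 against −0.50 from first dose; −0.05 to −0.25 against 0 from extension baseline (ρ 0.9 to 0.5).
- d = 0: no bias from first dose; −0.03 to −0.14 from extension baseline.
- d = 1: −0.07 to −0.36 against 0 from extension baseline.

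**4. A harsher scenario.** Assume CDASI mean 22, SD 8, half of patients responding with a 60% fall, cut-off 14 and reliability 0.7 to 0.9. The all-DM change is 0.5 × 0.6 × 22 = 6.6 points of improvement.

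- Arm B, response fully kept at Week 32: the subgroup shows −3.3 to −2.2 and loses 80% to 89% of responders. If 8 is the observed rather than the error-free SD, it shows −2.6 to −1.9 and loses 84% to 91%.
- Arm A, half the response lost on placebo and later regained (8 as the error-free SD): −6.5 to −6.7, close to the all-DM value.

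Across the scenarios with a drug effect, Arm B understates the all-DM change by between 6% (0.03/0.50) and 71% ((6.6 − 1.9)/6.6). The direction is stable; the size depends on the assumptions.

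**5. Check of the remedy.** In the step 3 model, selection on pre-treatment activity leaves Arm B's change from extension baseline at 0.00. Where the reference visit is also the selection visit (Arm A, Day 1), regression to the mean is (1 − ρ) × φ(1)/Φ(1) = (1 − ρ) × 0.288, or 0.03 to 0.14 SD; at d = 1 and ρ = 0.7 the subgroup shows −1.09. For Arm B, selection on Day 1 and reference at Week 16 are separate visits, and under equal correlations the artefact is nil.

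**The case against.** The strongest reply is that the plan never commits to the harmful use. Section 2.2.1 only permits periods reaching back into Study 003, and Section 3.1 makes Week 32 the extension baseline. Counted from there, this is an ordinary baseline subgroup with a fair question: does skin disease still present at entry improve? The same section uses extension baseline for patients on corticosteroids or immunosuppressants. The antibody parallel is also weak, because antibody status is not the outcome. The study is descriptive, Section 10 already summarises by prior sequence, and the SAP is still to be finalised.

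Most of this stands. The subgroup is legitimate for change within the extension, and no error rate is affected. What does not stand is that the problem is hypothetical: Section 10 says data will be summarised for all its groups from first dose and makes no exception for this subgroup.

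A reader might infer that patients whose skin cleared are dropped from the CDASI endpoint. They are not: the same bullet first lists all DM patients, and responders are counted there. A reader might also infer that improvement is understated in both arms. The documents do not support that for Arm A, which is selected after placebo.

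**Conclusion.** The point holds in a limited form. In summaries from the first KZR-616 dose, the extension-baseline subgroup understates Arm B improvement (Groups 2 and 3, and through Arm B the combined group) if the drug works. In Arm A the understatement may be small or nil, so the Group 1 versus Group 2 comparison in this subgroup is weakened. For change from extension baseline the subgroup is usable, with regression to the mean towards apparent improvement.

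The size cannot be determined from the documents. The SD-unit and point figures rest on assumed values for the mean, variability, cut-off, response and retention. The large losses of responders in the harsher scenario require full retention of response at Week 32, so they describe Arm B and should not be read as a general estimate. The all-DM summary is unaffected. The consequence is for interpreting one subgroup in a descriptive study of at most 24 PM and DM patients, where a few excluded responders could still move a mean.

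**What to change.** 1. For every CDASI summary that starts at the first KZR-616 dose in Study 003, define the active-skin subgroup by skin activity at Study 003 baseline, before any KZR-616 and at the same time point in both arms.
2. Keep the extension-baseline subgroup only for change within the extension. Show it by Study 003 arm beside all DM, label it as residual skin activity at extension entry, and do not use it for durability or overall skin efficacy.
3. In the SAP, state the instrument and cut-off that define active skin manifestations, and the reference visit for each CDASI summary.

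The cost is a line in the endpoint list and a few lines in the SAP, which is not yet final. It assumes that Study 003 recorded CDASI before treatment; Table 1 confirms only Week 32.

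There are two downsides. The pre-treatment subgroup will include patients with little skin disease left after Week 32. It also carries some regression to the mean of its own, mainly in Arm A, whose reference visit is the selection visit. This should be noted with the results.
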